10.3 Statistical Analysis

10.3.1 General Statistical Methods

The study data will be presented in tables, listings, and figures. Data will be summarized using descriptive statistics. The descriptive statistics for continuous variables will include mean, standard deviation, median, Q1 and Q3, minimum, maximum, and sample size. Categorical variables will be described with counts, percentages, and sample size. A 95% confidence interval may be presented, when necessary.

10.3.2 Analysis Set(s)

The study analysis will include all valid data collected from all participating subjects.

10.3.3 Analysis of Primary Endpoint

Data analysis for the data collection interval, which is defined as the 5 second period starting after a twelve (12) second technical delay from the time sampling occurs, will follow ISO80601-2-61, 2011, Annex EE and the FDA Guidance Document for Pulse Oximeters (FDA Guidance, March 4, 2013). Separate analysis will be performed for each sensor type.

The ARMS calculation is used as a means to define the SpO₂ Accuracy. Arms will be calculated as

$$Arms = \sqrt{\frac{\sum_{i=1}^n (DUT_i - Ref_i)^2}{n}}, \text{ where}$$

Ref_i = Reference CO-Oximeter Functional SaO₂ of data pair *i*

DUT_i = Device Under Test SpO₂ of data pair *i*

Study Title: U-TruSignal SpO₂ Testing in Neonates

Study No: 123.04-2017-GES-0002

The difference between SpO₂ and SaO₂ will be summarized using mean, minimum and maximum. Number of subjects and number of data pairs will also be presented.

A least squares regression of SpO₂ on SaO₂ will be performed and results be presented with a regression plot and table.

Bland-Altman graphical plots, error (SpO₂ – SaO₂) versus average SaO₂ will be generated with mean, and upper 95% and lower 95% limits of agreement according to Section 3 of “Agreement Between Methods Of Measurement With Multiple Observations Per Individual” by Bland and Altman in 2007 Journal of Biopharmaceutical Statistics. Individual test subjects will be color coded in the Bland-Altman graphical plot.

Data listed below will be excluded from analysis:

- Data with SaO₂ < 70%, tHb < 10g/L, MetHb > 2%, COHb > 3%;
- Draws with values smaller than -0.5% in any of the Hb values;
- Artefacts/other external error sources indicated by clinical documentation or derived from the collected data around sampling including but not limited to:
 - changes in sensor fit;
 - excessive movement during draw;
 - low perfusion (mod% < 0.5%);
 - irregular plethysmographic waveform or artefacts in the waveform;
- Data with error conditions on CO-Oximeter analysis indicated by clinical documentation e.g. air bubbles in syringe, clots, violation of hospital’s standard procedure;
- Data with error conditions on pulse oximeter;
- Unstable SpO₂ readings from the respective device under test:
 - SpO₂ max-min ≥ 4% in time window during 30 sec prior/after the blood sample;
 - SpO₂ max-min ≥ 8% in time window during 10 minutes prior to the blood sampling time;

A rationale will be provided for any data that is excluded from the data analysis.

10.3.4 Analysis of Secondary Endpoint

Invalid data will be characterized during the data collection interval, which is defined as the period in which SpO₂ is collected excluding annotated invalid data periods. Gaps in the data collection interval will be seen in the e-data file as invalid (negative number) as identified by GE engineering.

- Invalid data < 10%

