Study No: 123.04-2017-GES-0002

Objectives:	
Primary: To compare SpO₂ data from the U-TruSignal device to SaO₂ values from CO-Oximeter analysis of simultaneously drawn arterial blood.
 
Secondary: To demonstrate U-TruSignal collects substantially continuous SpO₂ measurements during a data collection interval, which is defined as the period in which SpO₂ is collected.
 
Safety: To collect safety information, including type and number of AE's, SAEs, and device issues.

Endpoints:	
Performance: The primary endpoint will be Accuracy Root Mean Square (ARMS), comparing the accuracy of SpO₂ values from the investigational device to SaO₂ values from CO-Oximeter analysis of simultaneously drawn arterial blood.
 
The secondary endpoint will be the percent of invalid data referred to as gaps per data collection interval.
 
Safety: Type and number of AEs, SAEs, and device issues.

Eligibility criteria:	
Inclusion criteria:
 
 1) Parents or legally designated representative (LDR) can understand and provide written informed consent; AND 2) Subjects are < 29 days old and requiring arterial blood samples per the site's standard of care. 
Exclusion Criteria:
 
 1) Neonates with injuries, deformities or abnormalities may prevent proper application of the sensor; 2) Neonates with inadequate heart pump function affecting blood circulation caused by identified cardiac or cardiovascular conditions such as patent ductus arteriosus, persistent pulmonary hypertension, septal defects, or congenital heart disease; 3) Neonates with mean arterial blood pressure < 20mmHg; 4) Neonates with congenital diaphragmatic hernia; OR 5) Neonates under High frequency ventilation therapy.
Sample size and Sites:	
This study is intended to collect blood samples from neonates under normal clinical conditions. The minimum number of subjects is 17 subjects. Maximum total enrollment for the study is 140 subjects. Subjects will be enrolled at 2 sites.

Study duration:	
The study is expected to last 24 months.

ADMINISTRATIVE STRUCTURE OF INVESTIGATION		
Clinical Affairs Project Manager (Sponsor Contact):	[name] Tel: [contact] E-mail: [contact]	GE Healthcare (GEHC) Address: [name] [name]

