3. STUDY OBJECTIVES AND ENDPOINTS

3.1 Purpose of the Study

The purpose of the study is to demonstrate proper function of the U-TruSignal device via clinical performance testing in a neonatal human subject population under standard clinical conditions. For the purposes of this study, proper function will be defined by accuracy (i.e. ARMS value), substantially continuous measurement abilities, and safety profile.

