3.2.2 Secondary Endpoint

The secondary endpoint will be the percent of invalid data, referred to as gaps, per data collection interval.

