5.3 Description of Study Procedures

The following are the steps to be performed:

- 1) To document the case, photographs of the position of the measurement sensors and other equipment may be taken at the request of the Sponsor at any point of the procedure, when necessary.
Note: photographs are taken in a way that the subject cannot be identified from the pictures.
- 2) Apply sensor(s) to the subject as appropriate. No more than one SpO₂ sensor placed on the same limb, and no sensor placed close to blood draw site/IV cannulation (same limb). Record site of sensor(s) placed on the CRF.
- 3) Allow the clinical environment and readings to stabilize.
- 4) Start data collection using the data collection tool.
- 5) Collect data using the data collection tool for a minimum of 10 minutes prior to routine arterial blood draw, per the data collection tool. Record possible accidental annotations in CRF.
Note: The arterial blood draw collected during this study will be performed according to the site's standard of care and will not be prescribed by the Sponsor.
- 6) When routine arterial blood draw is conducted, mark arterial blood draw time with data collection tool. The blood sample will be processed through hospital's standard procedure. Record possible accidental annotations in CRF.
- 7) After arterial blood draw, continue collecting data using the data collection tool for a minimum of 2 minutes. Record possible accidental annotations in CRF. Stop data collection.
- 8) Remove sensor(s) from the subject.
- 9) Monitor and record the following information using the data collection tool or recording on CRF during steps 4-7):
 - a. clinical status notes; i.e., frequent apnea, hemodynamic instability, abnormal heart rhythm, or other status;
 - b. environmental conditions such as changes in lightning conditions, ongoing care moving the neonate outside blood sampling, excessive clinical signs such as agitation, readjustment of a sensor; AND
 - c. notes regarding data collection such as accidental annotations.
- 10) Obtain results of the arterial blood draw and record possible errors during standard procedure for blood sampling and analysis.
- 11) Repeat Steps 1-10 up to 3 times to obtain a maximum of 6 data pairs, 3 data pairs per sensor aiming to collect equal data for each sensor.

Note: Alternate the sensors used; e.g., if TS-AF was used first, then TS-SE should be used at the next data collection.

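### Section 10.3.4 removes annotated periods that the plan never defines before computing percent invalid data, so the figure need not describe the interval named in the secondary objective

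*Combined protocol and SAP*

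**What the plan says.** The synopsis (Objectives) and section 3.1.2 set out to show substantially continuous SpO2 "measurements during a data collection interval, which is defined as the period in which" SpO2 is collected. Neither place carves anything out. Section 3.2.2 then states: "The secondary endpoint will be the percent of invalid data, referred to as gaps, per data collection interval".

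Section 10.3.4 gives the same term a narrower meaning. The interval is now the time in which SpO2 "is collected excluding annotated invalid data periods". Gaps are the negative numbers in the electronic file, as identified by the sponsor's engineers, and the section ends with a benchmark of under 10% invalid.

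Section 3.1 gives the endpoint its weight: "proper function will be defined by accuracy (i.e. ARMS value), substantially continuous measurement abilities, and safety profile".

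Section 5.3, step 9, tells staff to "record the following information using the data collection tool or recording on CRF during steps 4-7". The items include environmental ones, such as "ongoing care moving the neonate outside blood sampling, excessive clinical signs such as agitation, readjustment of a sensor", and clinical status, given as "frequent apnea, hemodynamic instability, abnormal heart rhythm, or other status". Accidental annotations are also to be noted. Section 6.1 repeats several of these for the CRF.

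**The concern.** The endpoint is a percentage of invalid data, and the analysis first removes periods labelled invalid. Unless the label is tied to something independent of the signal, the removal can take out part of what is being measured. Sensor readjustment shows the difficulty. A nurse may move a sensor during routine care, or may move it because the reading had gone. The first is outside disturbance. The second is the loss of continuity that the endpoint is meant to count. The plan does not separate them.

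Two analysts following section 10.3.4 could remove different periods and report different percentages, and a reader could not tell how much recording lay behind either. Under 10% is the only benchmark the plan gives for continuity, and section 2.1 says the results are intended for regulatory submission. What the percentage describes therefore matters even though section 10.1 says no hypothesis is tested.

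**Working it through.** **The text.** I looked for any section that settles which periods are removed, or makes the removal visible.

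- Section 5.3, step 9, and section 6.1 list what to record. They do not say which items make a period invalid, who decides, or when. Step 9 does not ask for start and stop times.
- Section 10.3.2 includes all valid data and does not define annotated periods.
- The exclusion list in section 10.3.3 is written for the primary analysis. Its closing sentence promises a rationale for excluded data. If it reaches this endpoint, it supplies a reason but no amount.
- Section 10.4 concerns documentation of missing data, not recorded time that the analyst removes.

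The gap in the text stands.

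**The arithmetic.** There is no figure to reproduce, because the 10% benchmark has no derivation. What can be shown is how far the two versions may differ. Let

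- r = reported percent invalid, after exclusion;
- a = share of the recording removed as annotated;
- f = share of the removed time that is gap;
- W = percent invalid over the whole recording.

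Then W = r(1 − a) + f·a. The documents give none of r, a or f, so all values below are assumed. Equal spacing of samples is also assumed, since no sampling rate is given.

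| r | a | W at f = 0 | W at f = 1 | f at which W = 10% |
|---|---|---|---|---|
| 5% | 5% | 4.75% | 9.75% | not reached |
| 5% | 10% | 4.5% | 14.5% | 0.55 |
| 5% | 25% | 3.75% | 28.75% | 0.25 |

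For example, with r = 5% and a = 10%, W = 0.05 × 0.90 + 0.10f, which is 0.045 at f = 0 and 0.145 at f = 1.

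The difference can run the other way. If the removed time held good signal (f = 0), a reported 12% with a = 25% gives W = 0.12 × 0.75 = 9.0%.

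**Smallest removal that could allow a crossing.** If all removed time is gap, W reaches 10% when a = (0.10 − r)/(1 − r):

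- r = 2%: 0.08/0.98 = 8.2%
- r = 5%: 0.05/0.95 = 5.3%
- r = 8%: 0.02/0.92 = 2.2%

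The shortest recording is 12 minutes, or 720 s: section 5.3 asks for data "for a minimum of 10 minutes prior to routine arterial blood draw" and at least 2 minutes after it. There the shares come to 58.8, 37.9 and 15.7 s. Check for r = 5%: 38 s of gap plus 5% of the remaining 682 s is 38 + 34.1 = 72.1 s, and 72.1/720 = 10.0%.

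In the other direction, with f = 0, a = 1 − 0.10/r. For r = 12% this is 16.7%, or 120 s of 720 s.

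The shares do not depend on recording length, but the seconds do. At about 30 minutes (1,800 s), the upper duration in the synopsis, the r = 5% case needs 0.0526 × 1,800 = about 95 s. These are limiting cases, not estimates.

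**The case against.** The best defence is that an analysis section may refine an objective. Section 10.3.4 states its exclusion in advance, and the plan uses this term locally: section 10.3.3 gives it a third meaning, a 5-second window after a 12-second delay. Section 3.2.2 adds no definition of its own. On that reading section 10.3.4 is the operational definition, and the benchmark was written for it. This is fair, and I do not call the two sections a flat contradiction. But an operational definition has to be operable, and the excluded periods are not specified.

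It can also be said that *annotated* implies a documented mark or note, and that discounting time when a carer is handling the infant is reasonable. Both points stand. They support keeping the version with exclusions, but do not replace the whole-recording figure.

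A reader might go further in three ways that the documents do not support:

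- **That the exclusion flatters the device.** The removed time may hold good signal, in which case the reported figure is too high.
- **That apnea or abnormal rhythm will be cut out.** Step 9 asks for these to be noted; no section calls them invalid.
- **That a decision turns on 10%.** No section attaches one.

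**Conclusion.** The point holds as a defect in definition and reporting. Following section 10.3.4 exactly, time without valid SpO2 can leave the percent-invalid figure, so that figure need not describe the interval in the objective and does not bound the share of the recording without a reading. Confidence in this is high, because it rests on the text alone.

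The size and direction are unknown. The two versions could fall on opposite sides of 10% in either direction, but only for some combinations of removed time and gap share, all of them assumed here. Nothing shows that a crossing is likely. The endpoint is secondary and descriptive, so the consequence is limited to how the continuity result can be read. This is an inexpensive improvement.

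**What to change.** In section 10.3.4:

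1. Report percent invalid over the full collected recording, matching the objective, beside the version that excludes annotated periods.
2. Limit the excluded periods to documented external events. Name the qualifying step 9 items before the gap data are examined, and identify the periods without reference to the SpO2 gap values.
3. Report the amount of time removed, with the reason, wherever timing was recorded.
4. State which of the two figures the benchmark of under 10% applies to, and show the other alongside it.

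The cost is some wording and one extra table. The whole-recording figure needs no new data: gaps are already negative numbers in the electronic file, which section 11.1.1 says is transferred to the sponsor. There are two real drawbacks. The whole-recording figure may look less favourable because it counts disturbance from care, although the second figure beside it shows that. And removed time will be incomplete for events noted only on the CRF. Appendix D records that version 1.0 was already active at the site, so for any recordings already made the events can be named before the gaps are examined, but not before collection.

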10.3.5 Safety Analysis

Safety events will be presented as a listing, and frequency of instances will be calculated. This will be conducted for all subjects.

10.4 Handling of Missing Data

Analysis will be based on collected data, and no imputation will be done for missing data. The Investigator is obligated to provide written documentation of any missing data to the Sponsor and to provide clarification upon Sponsor request if possible.

10.5 Deviation(s) from the Original Statistical Plan

Any changes or deviations from the original statistical plan specified in this protocol will be described and justified in the statistical analysis plan (SAP) and study final report, per ISO 14155:2011.

11. QUALITY ASSURANCE AND CONTROL

11.1 Data Management

Data management processes for handling study data will be maintained by the Sponsor.

11.1.1 Completion of Case Report Forms (CRFs)

The data reported on the CRFs (eCRFs) shall be derived from source documents and be consistent with these source documents. Paper CRFs and/or electronic CRFs (eCRFs) will be used to collect data. The Sponsor will provide CRFs (eCRFs) and train study staff on completion of CRFs (eCRFs) using Good Documentation Practices (GDP). CRF Completion Guidelines (CCG) may be provided by the Sponsor to help facilitate training.

CRFs (eCRFs) are to be completed as information becomes available at the site. CRFs (eCRFs) should be signed by indicated parties, in indicated area(s), to certify the contents of the form. The Principal Investigator is ultimately responsible for ensuring completion of CRFs (eCRFs).

If discrepancies are discovered on paper CRFs during monitoring, the Sponsor's representative will ensure that the study staff makes necessary corrections directly to the paper CRF(s) prior to collection.

The original copies of paper CRF shall be sent to the Sponsor after the study monitor has completed data verification. Photo copies of the paper CRF shall be kept by the site along with the study documents. Upon receipt of the paper CRF by the Sponsor, the Sponsor will review the data. A Data Clarification Form (DCF) may be provided to the site to correct or clarify discrepancies.

If a site discovers discrepancies after paper CRF collection, the site may notify the Sponsor and request data modification.

In the event that any discrepancies are discovered on the eCRF, whether during monitoring or during data review by the study team, a query will be raised, and the site shall make the correction within the electronic database, noting the reason for change. Data will be considered clean once all queries are answered and closed.

If the Sponsor discovers discrepancies on eCRFs, a query will be raised, and necessary corrections will be made by the site. The reason for any changes will be noted. All queries will be resolved prior to study completion.

There will be electronic data collected by the U-TruSignal data collection tool to which only authorized personnel will have access. Data collected by the data collection tool will be fully de-identified; i.e., all personal identifying information has been removed and replaced by using the subject identification number assigned to the subject. Electronic data will be transferred to GEHC as indicated in the Data Management Plan. A copy of this electronic data shall be provided to the site to which the site will store with the subject's study documents.

11.1.2 Data Handling and Record Keeping

All documents and data shall be produced and maintained in a manner that assures control and traceability.

Study Title: U-TruSignal SpO2 Testing in Neonates

Study No: 123.04-2017-GES-0002

11.1.3 Source Data and Documents

Source data includes information in original records, certified copies of original records of clinical findings, observations, or other activities for the study. Source documents for each subject must be retained throughout the investigation, including printed or electronic documents containing source data. Elements should include:

- **Source data and documentation** relevant to data recorded for subject screening and CRF corroboration.
- **Subject records** containing the completed ICFs, CRFs, and electronic data copied from the data collection tool.
- **Regulatory binder** containing the protocol and any subsequent amendments, EC submissions and approvals, blank ICF(s), and site logs.
- **Reference manuals** containing Investigator responsibilities, Sponsor, AE/SAE and informed consent guidelines, applicable study aids and training materials, and operator's manuals.

The Principal Investigator or institution shall provide direct access to source data during and after the clinical investigation for monitoring, audits, EC review, and regulatory authority inspections.

11.1.4 Archiving

All study data must be archived for the period defined by local law after study termination or premature termination of the clinical trial. No source documents or study records will be destroyed without Sponsor notification and approval.

12. MONITORING PLAN

In collaboration with the site, the Sponsor will ensure proper monitoring of the study to confirm that all the research requirements are met. Monitoring visits will oversee the progress of a clinical investigation and ensure that it is conducted, recorded, and reported in accordance with the protocol, written procedures, GCP ISO 14155:2011, and the applicable regulatory requirements.

12.1 Confidentiality and Data Protection

The Investigator affirms and upholds the principle of the participant's right to privacy, and the Investigator shall comply with applicable privacy laws. Especially, anonymity of the participants shall be guaranteed when presenting the data at scientific meetings or publishing data in scientific journals.

Individual subject medical information obtained as a result of this study will be considered confidential, and disclosure to third parties will be prohibited. Subject confidentiality will be further ensured by utilizing subject identification code numbers. For data verification purposes, authorized representatives of the Sponsor, a competent authority (CA), or an EC may require direct access to parts of the medical records relevant to the study, including subject medical history.

12.1.1 Storage of Images and Associated Health Data

Electronic data from the U-TruSignal Data Collector and associated data will be collected and disclosed to the Sponsor as part of this study. Fully de-identified data, which has had all personal identifying information removed, may be stored and used by the Sponsor indefinitely. The Sponsor and/or its authorized representatives may use any de-identified data collected in this study for future technology and engineering development, marketing purposes, education, regulatory submissions, publications, or other possible uses.

